Appendix H Product Labeling

Triathlon PSR Outcomes Study Stryker Clinical Study Protocol Version 1.1

List of Tables and Figures

TABLE 1: ACCEPTABLE ADDITIONAL DEVICES	8
TABLE 2: ACCEPTABLE ACCESSORY DEVICES	9
FIGURE 1 ADVERSE EVENT DECISION TREE	14

List of Abbreviations

ADE Adverse Device Effect

AE Adverse Event

BMI Body Mass Index

CFR Code of Federal Regulations
CPTi Commercially Pure Titanium

CSM Clinical Study Manager

EC Ethics Committee

eCRF Electronic Case Report Form

EDC Electronic Data Capture

GCP International Conference of Harmonization Good Clinical Practice

HIPAA Health Insurance Portability and Accountability Act
ICMJE International Committee of Medical Journal Editors

IRB Institutional Review Board

PI Principal Investigator

QOL Quality of Life

ROM Range of Motion

SAE Serious Adverse Event

SC Study Coordinator

SF-36 Short Form-36

TKA Total Knee Arthroplasty

UADE Unanticipated Adverse Device Effect

UHMWPE Ultra High Molecular Weight Polyethylene

Study Synopsis

Title	A prospective, post-market, multi-center evaluation of the clinical outcomes of the Triathlon Total Knee System using the Triathlon PSR Tibial Insert			
Short Title	Triathlon PSR Outcomes Study			
Protocol Number	103			
Phase	Post-market			
Methodology	This study is a prospective, post-market, non-randomized evaluation of the change between the preoperative and postoperative SF-36 outcomes in a consecutive series of primary total knee arthroplasty (TKA) patients who meet the eligibility criteria and received the			
	Triathlon Globalization Knee System.			
• Enrollment period of 24 months • Follow-up of each primary cemented TKA case to 10 years • Approximate 12-year total duration				
Number of Centers	2 - 8 centers			
	The SF-36 physical scores at 2 years for subjects receiving a cemented			
Hypothesis	Triathlon Total Knee with the Triathlon PSR insert is comparable with that of historical Triathlon PS cemented constructs.			
Objectives	 Primary: To compare the SF-36 physical scores for subjects receiving a cemented Triathlon Total Knee with the Triathlon PSR insert to scores for subjects who received historical Triathlon PS cemented constructs at 2-years postoperative. Secondary Objectives: To evaluate the change between the preoperative and postoperative EQ-5D scores. To evaluate range of motion (ROM) at 2-years postoperative. To evaluate the survivorship of the Triathlon PSR insert at 10- 			
	years postoperative.			

Subject demographics and medical histories are collected (age, sex, primary diagnosis, BMI, comorbidities, medications used, smoking history, alcohol use, education level, employment status, confounding orthopedic problems, etc.). 2011 KSS will be presented with respect to improvement from preoperative scores. The Forgotten Joint Score (FJS) will be collected at 2-years **Additional Data** postoperative. Collection Assessment of radiographic outcomes using Anteroposterior (AP). Mediolateral (ML) and Merchant radiographs. A Follow-up Questionnaire is administered to assess patient satisfaction, pain, study device survivorship and capture adverse events (AEs). Collection and evaluation of device related AEs and unanticipated adverse device effects (UADEs). **Primary Objective:** The mean SF-36 physical score at 2-years postoperative will be compared to 47.3 (the reference score from the historical control) with a non-inferiority margin of 2.5 points. • A two sided 90% confidence interval will be computed for the mean SF-36 score. If the lower bound is greater than 44.8, the non-inferiority hypothesis holds. Statistical **Secondary Objectives:** The change of EQ-5D from preoperative to postoperative will be Methodology compared using a paired t-test. The mean ROM at 2-years postoperative will be compared to the reference value from the historical control (124 degrees) with an error margin of 5 degrees. A TOST (two one-sided test) will be used to test the difference. A Kaplan-Meier survival curve for all-cause revision/removals will of the Triathlon PSR insert will be displayed at 10-years postoperative. The survival rate will also be presented with a twosided 95% confidence interval. A total of 250 cases (knees) will be enrolled in the study. **Number of Cases** Cases must receive the appropriate study device to count toward enrollment.

Required Components:

• Triathlon PSR Insert (X3 EtO)

Study Device

Compatible Stryker tibial baseplates, femoral components, and patellar components must be used in accordance with the applicable Instructions for Use and Surgical Technique(s). All components must be cemented with respect to the bone.

Additionally, a variety of compatible Triathlon device accessories may be used, as indicated in the surgical protocol.

Inclusions:

- A. Patient has signed an IRB/EC approved; study specific Informed Patient Consent Form.
- B. Patient is a male or non-pregnant female, skeletally mature, age 18-75 years at time of study device implantation.
- C. Patient has a diagnosis of Non-Inflammatory Degenerative Joint Disease (NIDJD).
- D. Patient is a candidate for primary cemented total knee replacement.
- E. Patient is willing and able to comply with postoperative scheduled clinical and radiographic evaluations and rehabilitation.

Exclusions:

1. Patient has a Body Mass Index (BMI) > 45.

2. Patient is already participating in the study for a contralateral total knee replacement.

- 3. Patient has a diagnosis of avascular necrosis or inflammatory arthritis.
- 4. Patient has an active or suspected latent infection in or about the affected knee joint at time of study device implantation.
- 5. Patient has any mental or neuromuscular disorder which would create an unacceptable risk of prosthesis instability, prosthesis fixation failure, or complications in postoperative care.
- 6. Patient has a compromised bone stock which cannot provide adequate support to the prosthesis.
- 7. Patient is immunologically suppressed or receiving steroids in excess of normal physiological requirements (e.g. > 30 days).
- 8. Patient is diagnosed with lumbar radicular pain.
- 9. Patient has severe instability of the knee joint secondary to the absence of collateral ligament integrity and function.
- 10. Patient has a known sensitivity to device materials.
- 11. Patient is a prisoner.

Reference Therapy

Inclusion/Exclusion

Criteria

Reference Control: Triathlon PS Cemented Femur with PS Insert (X3 and N2Vac), Triathlon Primary Cemented Baseplate, and Triathlon Patellar Component (X3 and N2Vac)

ClinicalTrials.gov Identifier: NCT00957021

CONFIDENTIAL

Evaluation Schedule

Evaluation	Preop X-rays (-1 yr) CRFs (-4 mos)	Intraop	6 wks (± 3 wks)	1 yr (± 2 mos)	2 yrs (+ 2 mos)	3 yrs (+ 3 mos)	4 yrs (+ 4 mos)	5 yrs (+ 4 mos)	Annually 6, 7, 8, 9 yrs (+ 4 mos)	10 yrs (+ 4 mos)
Inclusion/ Exclusion	х									
Demographics & Medical History	х									
Surgical Details		х								
Preoperative KSS	х									
Postoperative KSS			х	х	х			х		х
FJS					х					
SF-36	х		х	х	х	х	х	х		х
EQ-5D	х		x	x	х	х	x	х	х	х
Radiographs: AP/ML/Merchant View	х		х	х	х			х		х
Follow-up Questionnaire						х	х		Х	

X: Evaluation is required for all cases.

KSS: The 2011 KSS is a standardized instrument with both patient-reported outcomes and surgeon completed sections that evaluate function, satisfaction, expectations and range of motion.

FJS: The FJS is a 12-item questionnaire assessing a patient's ability to forget his/her artificial joint in everyday life.

SF-36: The SF-36 is a standardized 36 item patient reported outcome questionnaire that evaluates general health and well-being.

EQ-5D: The EQ-5D is a standardized instrument for use as a measure of health outcome.

Follow-up Questionnaire: The Follow-up Questionnaire is a short patient questionnaire intended to provide information on patient satisfaction, pain, study device survivorship and AEs.

AP View: Radiographic view of the knee containing the femoral component, medial and lateral femoral epicondyles, and tibial component.

ML View. Radiographic view of the knee containing the patella, patellar component, and overlapping posterior condyles of the femoral and tibial component.

Merchant View: Radiographic view of the knee containing the articular surface of the patella and femur.

1 Introduction

This document is a protocol for a human research study. This study will be conducted in compliance with the protocol, Good Clinical Practice (GCP) Standards, Health Insurance Portability and Accountability Act (HIPAA) requirements, applicable Food and Drug Administration (FDA; 21 Code of Federal Regulations (CFR)), European, and International Organization for Standardization (ISO) regulations (ISO 14155).

1.1 Background

Primary total knee arthroplasty (TKA) has consistently shown to reliably relieve pain and improve function for patients suffering from end-stage knee arthritis.¹

The Triathlon Knee system is designed to meet patients' reasonable expectations for patient satisfaction and return to function. As a next-generation knee replacement, the Triathlon Knee System closely mimics natural knee motion providing mobility with stability through or exceeding 150° of flexion². The Triathlon design criteria are realized through component features including an anatomic, deep flexion radius, flared posterior condyles, a patented Rotary Arc and an anatomic patellofemoral track.

Studies of kinematics and biomechanics have identified a constant radius in natural knee motion centered about the transepicondylar axis^{3,4,5}. The Triathlon Knee System is the first of its kind with a patented anatomic radius. Centering the anatomic radius about the transepicondylar axis provides ligament isometry, not only in full extension and 90° of flexion, but through the entire range of motion. The anatomic radius is designed to mimic natural knee motion, enhancing stability and mobility in activities such as descending and ascending stairs or any similar activity requiring stability at deep flexion angles.

With the number of patients receiving TKA rising annually, it has become increasingly important to accommodate cultural needs to achieve increased rotation in deep flexion for safe, deep knee bending. Posterior-stabilized (PS) implants have been shown to allow for higher flexion than cruciate-retaining (CR) implants making them better candidates to support the desired range of motion⁶.

Axial rotation is an important consideration when looking to develop safe, high flexion implants. Natural axial rotation is approximately 30° through 120° of flexion. Replicating this degree of axial rotation in high-flexion implants is important in supporting the extensor mechanism at deep flexion and maximizing range of motion⁷.

The Triathlon (PSR) tibial insert has been designed to accommodate the need for deep knee bending by reducing rotational constraint in deep flexion. The insert maintains key Triathlon PS design features including the post size and location, 45° tibial post-femoral cam engagement, Rotary Arc & Sagittal profile, and 10°-110° single radius flexion. The posterior reduction of the PSR insert allows the knee to better replicate the degree of normal axial rotation during deep knee bending. The Triathlon PSR insert is cleared for use under K190402. See **Appendix A** for clearance letters.

2 Clinical Study Plan

2.1 Study Design

A prospective, post-market, multi-center design will be employed. Radiographs will be assessed by an independent reviewer.

2.2 Study Centers

Cases will be enrolled at two to eight centers. There is no maximum limit to the number of cases that a center may enroll. In the event that a center far exceeds enrollment at other centers, Stryker may ask the center to cease enrollment so as not to skew the data. All participating centers will comply with the federal regulations regarding patient informed consent and Institutional Review Board (IRB) or Ethics Committee (EC) approval. Non-compliance of a study center may result in termination of the center's participation in the study.

2.3 Number of Subjects

Cases will be enrolled until at least 250 cases have received the Triathlon Total Knee System with the Triathlon PSR insert.

3 Device Description

3.1 Study Device

All cases in this post-market study will receive a Triathlon PSR insert.

The Triathlon PSR insert is intended to be used as a component in primary TKAs receiving a Triathlon Total Knee System. Fabricated from X3 ultra-high molecular weight polyethylene (UHMWPE), the insert is designed to reduce rotation constraint at deep flexion. The insert must be used with a compatible Triathlon baseplate, PS femoral component, and patellar component. For the purposes of the study, all components must be cemented with respect to the bone.

The Triathlon PSR insert is available in 9 sizes (Size 0-8) and 8 thicknesses (9, 10, 11, 12, 14, 16, 19, and 22 mm). Only Sizes 1-8 will be used in this study. All Triathlon PSR inserts will have a catalog number with the following format:

8532-G-XXX-E

The full listing of permissible Triathlon PSR catalog numbers may be found in **Appendix B**.

3.2 Additional Devices

The following **Stryker compatible** devices are to be used, according to this study protocol:

Table 1: Acceptable Additional Devices

Required Additional Components		
5515-F-XXX	Triathlon PS Cemented Femur	
5520-B-XXX	Triathlon Primary Cemented Tibial Baseplate	
5521-B-XXX	Triathlon Universal Tibial Baseplate	
5550-G-XXX	Triathlon Patellar Component, Symmetric (X3)	
5550-G-XXX-E	Triathlon Patellar Component, Symmetric (X3 EtO)	
5550-L-XXX	Triathlon Patellar Component, Symmetric (N2Vac)	
5551-G-XXX	Triathlon Patellar Component, Asymmetric (X3)	
5551-G-XXX-E	Triathlon Patellar Component, Asymmetric (X3 EtO)	
5551-L-XXX	Triathlon Patellar Component, Asymmetric (N2Vac)	

Any on-label, compatible accessories may also be used. This includes, but is not limited to:

Table 2: Acceptable Accessory Devices

Acceptable Additional Components					
5575-X-000 Triathlon Femoral Distal Fixation Pegs					
5540-A-YYY	Triothlan Famoral Diatal Augment 9	5 mm			
5541-A-YYY	Triathlon Femoral Distal Augment & Locking Screws	10 mm			
5542-A-YYY	Locking Screws	15 mm			
5543-A-Y00	Triathlon Femoral Posterior Augment &	5 mm			
5544-A-Y00	Locking Screws	10 mm			
5545-A-YYY	Triothlan Tibial Augment	5 mm			
5546-A-YYY	Triathlon Tibial Augment	10 mm			
5549-A-1YY	Triothlan Tibial Cana Augment	Symmetric			
5549-A-2YY	Triathlon Tibial Cone Augment	Asymmetric			
5560-S-YYY	Triathlon Cemented Stem				
5565-S-0YY	Triathlon Fluted Stem	100 mm			
5566-S-0YY	Thathlon Fluted Stelli	150 mm			
5570-S-0Y0	Triathlon Offset Adaptor				
5571-S-0YY Triathlon Stem Extender					

The compatible Stryker components are listed in the surgical protocol and **Appendix B**.

In the case of any uncertainty regarding device compatibility, the current version of the Triathlon PS surgical protocol should be reviewed.

4 Study Procedures

4.1 Subject Recruitment and Screening

Patients will be recruited at the study centers during preoperative visits through normal referral patterns. Advertising for the study at each center will be at the discretion of the investigator. All handouts, brochures, advertisements, etc. must be approved by the IRB/EC prior to the dissemination of any recruitment materials to potential subjects.

During the preoperative visit, patients that are possible candidates for this study will be screened to determine if they meet the inclusion/exclusion criteria. If the patient is a candidate, the investigator will propose participation in the study to the patient, according to GCP guidelines. Patients must sign an IRB/EC approved Informed Patient Consent Form prior to participation in the study, as well as prior to any data collection.

4.2 Patient Informed Consent and Guidelines

All patients for this study will be provided an Informed Patient Consent Form describing this study and providing sufficient information for them to make an informed decision about their participation. The Informed Patient Consent Form must contain all elements required by the FDA under 21 CFR Part 50, in addition to any other elements required by state, local and institutional policies. For international sites, the applicable country regulations are required. See **Appendix C** for a copy of the Model Informed Patient Consent. This will be submitted with the protocol for review and approval by the IRB/EC for the study. All patients must provide written consent after having had adequate time to consider their participation in the study. The formal consent of a patient, using the IRB/EC approved Informed Patient Consent Form, must be obtained before that patient is submitted to any protocol related procedures that are not part of normal care. Written documentation of consent must be provided on the Informed Patient Consent Form's signature page in addition to a note in the patient medical records indicating the date that consent was obtained. The investigator-designated research professional obtaining the consent must also sign this Informed Patient Consent Form. The patient or his/her legal representative should receive a signed copy of the Informed Patient Consent Form, according to GCP guidelines.

The procedure for obtaining informed consent is outlined below:

- Use a current IRB/EC approved copy of the Informed Patient Consent Form.
- Review thoroughly with the patient, allowing adequate time to consider participation in the study and ask questions, before having them sign.
- After the patient has consented to the procedures, ensure he/she signs and dates the Informed Patient Consent Form.
- The person obtaining consent also signs and dates the signature page.
- Provide a copy of the signed Informed Patient Consent Form to the patient.
- If required, provide the hospital with a copy of the signed Informed Patient Consent Form.
- Maintain the signed original in the patient's study chart.

4.3 Early Withdrawal of Subjects

When and How to Withdraw Subjects

In the event that the subject is discontinued by the investigative center prior to the final study evaluation, the subject will be notified by the center that he/she is no longer in the study and a Study Termination eCRF will be completed.

The following is a list of reasons for which subjects may be withdrawn and the date of termination that should be used on the Study Termination eCRF in each situation. This list is not all inclusive:

Termination Reason Date of Termination

Death Date of death

Investigative center termination Date of study close-out visit

Lost to follow-up Date Stryker termination approval given

Voluntary withdrawal Date subject notified center of withdrawal

Revision/removal of study device Date of revision/removal procedure

Study device not implanted Date of surgery

Surgery not performed Date Stryker termination approval given

At the time of study surgery, it is required that the following components are implanted to be included in the analysis:

Triathlon PSR Tibial Insert

Compatible Triathlon Tibial Baseplate

Compatible Triathlon PS Femoral Component

o Compatible Patellar Component

All components must be cemented with respect to the bone.

Exchange of the Triathlon PSR Tibial Insert for any reason constitutes a failure and study termination for the subject.

If revision of any other component occurs during the study, the event does not constitute a failure or study termination.

If the subject fails to return for his/her follow-up appointments, every effort should be made to contact the subject to assess his/her health status. If, after attempting to contact the subject through three documented phone calls and a certified letter, the subject still does not respond, he/she will be considered lost to follow-up. A Study Termination eCRF will be completed only after notifying Stryker of the subject's status and being given approval to terminate.

In the event a subject does not have surgery, Stryker should be contacted to discuss if/when the surgery will be rescheduled. Preoperative data must be current within 4 months of the study surgery and will need to be re-collected if the surgery is rescheduled more than 4 months from the initial data collection. If the surgery is not to be rescheduled or if the subject is no longer

considered an appropriate study candidate, a Study Termination eCRF may be completed only after notifying Stryker of the subject's status and after Stryker has given approval to terminate.

When a subject completes the study according to protocol at the final study evaluation, a Study Termination eCRF will be completed.

5 Study Details

5.1 Study Objectives and Evaluation Schedule

The primary and secondary study objectives, as well as additional data collection are listed in Objectives and Additional Data Collection sections of the Study Synopsis (pages 8 and 9) For the evaluation schedule, please reference page 12.

5.2 Radiographic Outcomes

Radiographs will be taken and collected in the anteroposterior (AP), mediolateral (ML), and merchant views for the preoperative, 6-week, 1-, 2-, 5, and 10-year intervals. The suggested radiographic technique for the views required is included in **Appendix D**.

Radiographs will be evaluated by an independent reviewer throughout the course of the study. Parameters for radiographic failures will follow the guidelines that have been set by the Knee Society⁸. Radiographic analysis of the tibial component will employ seven zones (Zone 1 – Zone 7) in the AP view and three zones (Zone 1 – Zone 3) in the lateral view. Radiographic analysis of the femoral component will employ seven zones (Zone 1 - Zone 7) in the lateral view. Radiographic analysis of the patellar component will employ five zones (Zone 1 – Zone 5) in the merchant view. Numerous parameters will be reviewed including radiolucency, gaps and subsidence. Radiolucency in at least 50% of a zone and measuring at least 1 mm in width is defined as radiolucency present. Subsidence is defined as settling of the prosthetic component in bone and, for this study, is measured by looking at the change in position of the tibial baseplate with reference to a bony landmark (usually the very margin of the tibia) between visit

intervals. Cases that present with tibial baseplate subsidence of greater than 5 mm or at least 2 mm radiolucencies in all zones within a single view will be considered radiographic failures.

6 Adverse Events

6.1 Reporting of Adverse Events

The AE reporting requirements for this study are as follows:

[figure not shown]
- All AEs that meet the definition of serious (see page 22) and occur within the perioperative period (intraoperative to hospital discharge) to 90 days postoperative
- All AEs related to the operative site, regardless of seriousness or time of occurrence

On postoperative functional evaluations, investigators and SCs will be prompted to question subjects as to whether they have seen a doctor for any reason, been hospitalized for any reason or have a current impediment to their function.

For the 6-, 7-, 8-, 9-year intervals, only a Follow-up Questionnaire will be administered. SCs will be responsible for following up with the subjects regarding any questionable responses received on the Follow-up Questionnaire. If it is determined upon this further investigation that a protocoldefined AE has occurred, the SC will be responsible for completing an AE eCRF, submitting the event to Stryker, and reporting the event to the IRB as required.

The following decision tree facilitates identification of AEs for which reporting is required under this study protocol:

Figure 1. Adverse Event Decision Tree

General Physical Examination Findings

At screening for inclusion into the study, any clinically significant abnormality should be recorded as a preexisting condition and reported on the Demographics eCRF. From the time of consent forward, any new clinically significant findings or abnormalities that meet the definition of a protocol defined AE must also be recorded and documented as an AE.

Adverse Event Reporting Period

The study period during which AEs must be reported is normally defined as the period from the initiation of any study procedures to the end of the study treatment follow-up. The start of study procedures is considered to be the point of consent. Any AEs which fit the protocol defined reportable events must be reported from the time of consent until study completion.

At each contact with the subject the investigator must seek information on AEs by specific questioning and, as appropriate, by examination. Information on protocol defined AEs should be recorded immediately in the source document and also in the appropriate AE module of the eCRF. All clearly related signs, symptoms and abnormal diagnostic procedure results should be recorded in the source document and grouped under one diagnosis, as appropriate. The clinical course of each event should be followed until resolution or until it is determined at the end of the study that the AE will not resolve.

All operative site events occurring at any time as well as all serious adverse events (SAEs) occurring within the perioperative period to 90 days postoperative will be collected and compared to published data. It is expected that the AE rates reported for the Triathlon Total Knee with the Triathlon PSR insert will be comparable to those for historical Triathlon PS cemented constructs.

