6.4 Recording of Adverse Events

All protocol defined AEs occurring during the study period must be recorded; this includes events that occur between visit intervals. The clinical course of each event should be followed until resolution or stabilization.

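### Insert exchange ends study participation on the day of surgery, and the plan does not say how open or later adverse events, or a 2-year SF-36 still due, are then collected

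*Combined protocol and SAP*

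**What the plan says.** **When a subject leaves.** Section 4.3 states: "Exchange of the Triathlon PSR Tibial Insert for any reason constitutes a failure and study termination for the subject". Its list of termination reasons and dates has the entry "Revision/removal of study device Date of revision/removal procedure". Revision of a different component is treated the other way: "If revision of any other component occurs during the study, the event does not constitute a failure or study termination".

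**How long adverse events (AEs) are followed.** There are two wordings.
- Section 6.1: "The clinical course of each event should be followed until resolution". The sentence goes on, so that in full each event is to be "followed until resolution or until it is determined at the end of the study that the AE will not resolve".
- Section 6.4: "The clinical course of each event should be followed until resolution or stabilization".

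**Which AEs are reportable, and when.** Section 6.1 lists "All AEs related to the operative site, regardless of seriousness or time of occurrence" and, separately, serious AEs up to 90 days after surgery. On the reporting period it says: "Any AEs which fit the protocol defined reportable events must be reported from the time of consent until study completion".

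**What is recorded at an exchange.** An AE that leads to reoperation or revision goes to the sponsor within 24 hours with an eCRF and source documents (Section 6.3). The insert may be retrieved and analysed (6.3.2). Insert revision or removal is the 10-year Kaplan-Meier event (8.1.2), and revision or removal of any component is a safety parameter (8.2.1).

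**Analysis.** The primary and secondary analyses use non-censored subjects available for the 2-year evaluation (8.4.4). Nothing missing is imputed (8.3).

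**The concern.** Exchange of the study insert triggers the end of participation, yet it is also an event whose aftermath a safety reader would want to see. An AE that leads to an exchange may still be open on the day of surgery, and the same knee can have further operative-site events or another revision. Section 4.3 closes the subject's participation on that day, and no scheduled SF-36, EQ-5D, ROM, radiograph or questionnaire is provided for afterwards. The AE sections ask for follow-up and reporting without saying whether they still apply once the subject has been terminated. Sites could reasonably act differently.

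Two things are at stake. First, the later course of events after insert exchange may not be collected, while subjects with another component revised stay under observation. Second, a subject exchanged before 2 years has no 2-year SF-36 physical score (PCS). If such subjects score lower, their absence moves the primary mean towards non-inferiority, and no sensitivity analysis can recover data that were never collected.

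**Working it through.** **1. The sections side by side, for a subject whose insert is exchanged**

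| Question | Section 4.3 | Section 6.1 | Section 6.4 |
|---|---|---|---|
| When does participation end? | Day of the procedure | Reporting runs to study completion; term not defined for this subject | Not stated |
| Is an open AE followed afterwards? | Not stated | To resolution, or a judgement at the end of the study; term not defined | To resolution or stabilisation; no end-of-study alternative |
| Is a later operative-site AE recorded? | Not stated | Yes whatever its timing, but up to study completion | Events in the study period |

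Section 4.3 also separates subjects discontinued before the final evaluation from those who complete the study at that evaluation. In the protocol's own vocabulary, completing the study is therefore different from being terminated early. An exchange within 90 days of surgery would raise the same question for the 90-day window for serious AEs.

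**2. The plan's own sample size**

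Inputs from Sections 8.1.1 and 8.4.2: SD 10.7, margin 2.5, one-sided 5% (the lower limit of a 90% two-sided interval), power 95%, loss 20%.

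- Normal approximation: n = (10.7 × (1.645 + 1.645) / 2.5)² = 198.3, so 199.
- Noncentral t: n = 200, with power 0.9503.
- Inflation for loss: 200 / 0.8 = 250.

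The plan's 200 and 250 are reproduced.

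**3. Size of the effect on the primary mean**

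The documents give neither an exchange rate nor a post-exchange PCS, so both are assumed. Let r be the proportion exchanged before 2 years and d the number of points by which those subjects score below the others. Leaving them out raises the observed mean by r × d.

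Power with them included is calculated at N = 200, a true shortfall of r × d from 47.3, and SD = √(10.7² + r(1 − r)d²).

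| r | d | Shift r × d | Share of 2.5 margin | Power if included |
|---|---|---|---|---|
| 1% | 10 | 0.10 | 4% | 93% |
| 2% | 10 | 0.20 | 8% | 91% |
| 3% | 10 | 0.30 | 12% | 89% |
| 1% | 15 | 0.15 | 6% | 92% |
| 3% | 15 | 0.45 | 18% | 84% |

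A wider range (r from 1% to 5%, d from 5 to 15) gives shifts of 0.05 to 0.75 points, 2% to 30% of the margin, with power of about 94% to 71%.

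**4. Number of subjects**

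Assuming 2% to 6% exchanged by 10 years: 250 × 0.02 = 5 and 250 × 0.06 = 15.

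**The case against.** The strongest reply is that there is no contradiction. If the end of the study and study completion mean the subject's own termination, Sections 4.3 and 6.1 agree. The phrase on operative-site events stands next to a 90-day limit for other serious AEs and may mean only that the 90-day limit does not apply to them. Section 4.3 gives a date for a form; it does not say that an open AE record closes on that date. Ending follow-up at failure of the device under study is also a legitimate design choice.

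This reading is possible but weak. Section 6.4 has no end-of-study alternative, and Section 4.3 itself distinguishes early termination from completion. Even if the reading is accepted, the terms are undefined where it matters. But the objection does rule out four stronger inferences that a reader might draw:

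- *The sections cannot both be followed.* Not shown. The Section 6.1 sentence carries an end-of-study alternative, so the sections are unreconciled rather than incompatible.
- *The failures are never recorded.* Not so. The AE, the revision and the survivorship event are captured, and the insert may be analysed. What lacks a route is the later course.
- *These are the worst device failures.* The trigger is exchange for any reason, without grading by severity.
- *AE rates are biased low against historical data.* Not shown. If AEs are tabulated per subject, an exchanged subject with a reported operative-site event is already counted. The comparison also depends on whether the historical and published series followed subjects after revision, which the documents do not say.

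It is also correct that collecting the SF-36 after exchange changes nothing unless an analysis uses it, because Section 8.4.4 defines the set.

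**Conclusion.** The concern holds as a gap between Sections 4.3, 6.1 and 6.4. Insert exchange is an explicit termination dated to the procedure, and the plan provides no collection for the later course of the event, for later operative-site events or re-revision, or for a 2-year SF-36 when exchange comes first. A subject exchanged before 2 years is then outside the per protocol set, without imputation.

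The effect on the primary endpoint is probably modest and can be sized only by assumption: 0.1 to 0.45 points (4% to 18% of the margin) for 1% to 3% exchanged and 10 to 15 points lower. If exchanged subjects do score lower, the shift favours non-inferiority. The loss of safety information cannot be sized from the documents. The change is worth making because it costs little, not because the primary conclusion is shown to be unsafe.

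**What to change.** 1. Reconcile Sections 4.3, 6.1 and 6.4. Define the end of the study and study completion, and state whether they refer to the subject or to the trial.
2. In Section 4.3, separate device failure from the end of data collection. Exchange remains the survivorship event. AEs open at exchange are followed to resolution or stabilisation, and later operative-site AEs, including re-revision, are recorded and reported separately from pre-exchange events.
3. Where exchange occurs before 2 years, still collect the 2-year SF-36.
4. Add a sensitivity analysis of the primary endpoint that includes these subjects, alongside the analysis on the Section 8.4.4 population. In the same edit, confirm that exchanges before 2 years enter the Kaplan-Meier analysis, since Section 8.4.4 ties the secondary analyses to subjects available at 2 years.

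**Cost.** Protocol and consent wording, and continued contact with a small number of subjects (5 to 15 under the assumed 2% to 6%). AE or SF-36 figures may look slightly less favourable.
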